7 STATISTICAL METHODOLOGY

7.1 General Considerations

For continuous variables, descriptive statistics will include the number of subjects (n), mean, standard deviation, median, minimum and maximum. When needed, the use of other percentiles (e.g., 10%, 25%, 75% and 90%) will be mentioned in the relevant section. In addition, for continuous PK parameters, the coefficient of variation will be calculated and for C_{max} and AUC the geometric mean will also be calculated. Frequencies and percentages will be displayed for categorical data. Percentages by categories will be based on the number of subjects with no missing data, i.e. will add up to 100%. Kaplan-Meier survival curves will be displayed for time-to-event variables and median survival time will be estimated with 2-sided 95% confidence interval (CI).

Safety analysis and other summaries based on SAF will be presented by actual treatment received. Pharmacokinetic summaries based on will be presented by actual treatment received. For subjects with dose change, actual treatment refers to the first dose received before dose change.

All data processing, summarization, and analyses will be performed using SAS[®] Version 9.3 or higher on Unix. Specifications for table, figure, and data listing formats can be found in the TLF specifications for this study.

Baseline is defined as the last available measurement prior to the first dose of study drug. Unless otherwise specified, all summaries and analysis will be presented by phase.

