1.2.3.2 Clinical Pharmacokinetics and Pharmacodynamics

In study 2215-CL-0101, a phase 1/2 study in patients with relapsed/refractory AML, FLT3 mutational status was collected locally from the patient's record.

With regards to gilteritinib pharmacokinetics, median t_{max} was observed between 2 and 6 hours following single and repeat dosing. At a dose of 120 mg, the median C_{max} at day 15 was approximately 282 ng/mL and the median AUC at day 15 was approximately 6180 ng·h/mL. The estimated $t_{1/2}$ across dose levels based on R_{ac} ranged from 45 to 159 hours. Approximately dose proportional pharmacokinetics were observed following once daily administration of gilteritinib over the range evaluated (20 to 450 mg).

The effect of gilteritinib on the pharmacokinetics of midazolam, a CYP3A4 substrate, was investigated in patients with relapsed/refractory AML. Midazolam exposure was comparable when midazolam was administered alone or in combination with gilteritinib. The results suggest coadministration of gilteritinib and a CYP3A4 substrate is not expected to result in a clinically-relevant drug-drug interaction.

An assessment of the effect of gilteritinib on the pharmacokinetics of cephalexin, a MATE1 substrate, was also performed in patients with relapsed/refractory AML. Cephalexin exposure and renal excretion were comparable when cephalexin was administered alone or in combination with gilteritinib. These results indicated a clinically-relevant interaction is not expected when gilteritinib is coadministered with a MATE1 substrate.

The potential for drug-drug interactions was investigated in healthy subjects or patients with relapsed/refractory AML. The effect of ITZ (a strong CYP3A4 inhibitor), FLZ (a moderate CYP3A4 inhibitor) and RIF (a strong CYP inducer) on the pharmacokinetics of gilteritinib, a CYP3A4 and P-gp substrate, were evaluated in healthy adult subjects. Coadministration of gilteritinib with ITZ significantly increased gilteritinib exposure (approximately 2.21-fold) via a reduction in CL/F. As anticipated, a smaller increase in gilteritinib systemic exposure (approximately 1.43-fold) was observed following coadministration gilteritinib with FLZ. Furthermore, RIF significantly decreased gilteritinib systemic exposure (approximately 70%). In summary, coadministration of gilteritinib with a strong CYP3A4 inhibitor or inducer may result in significantly greater or lesser, respectively, gilteritinib systemic exposure.

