2.1.2 Secondary Objectives

The secondary objectives are to:

- Characterize the pharmacokinetics of gilteritinib and its active metabolites (if appropriate) when given in combination with atezolizumab.
- Evaluate the safety and efficacy of gilteritinib in combination with atezolizumab in terms of:
 - Gilteritinib trough plasma concentrations (C_{trough})
 - CR rate
 - CR with partial hematologic recovery (CRh)
 - Best response rate (CRc + PR)
 - Duration of remission
 - Event-free Survival (EFS)
 - OS
 - AEs, clinical laboratory results, vital signs, ECGs and Eastern Cooperative Oncology Group (ECOG) performance status scores

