Subjects will be administered treatment until discontinuation criterion is met. If 1 treatment is discontinued due to toxicity, the subject may continue on the other as monotherapy until discontinuation criteria is met. Subjects will have an (EOT) visit within 7 days after last dose of study drug, followed by a 30-day follow up for safety, after which the subjects will enter the long-term follow-up period of up to 3 years for collection of subsequent AML treatment, remission status and survival (cause of death and date of death).

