5.1.4 Previous and Concomitant Treatment (Medication and Non-Medication Therapy)

All medications and concomitant treatments administered from 28 days prior to cycle 1/day 1 through the EOT Visit must be recorded in the electronic case report form (eCRF).

Concomitant medications should be collected for reported or ongoing AE/serious adverse events (SAEs) through 30 days after the last dose of study drug for subjects who have discontinued treatment. For subjects who undergo HSCT, concomitant medications should be collected for reported or ongoing AE/SAEs through start of conditioning treatment or 30 days after the last dose of study drug, whichever comes first. Treatment with concomitant drugs that are strong inducers of CYP3A are prohibited. Treatment with concomitant drugs that are strong inhibitors or inducers of P-gp and concomitant drugs that target serotonin 5HT_{2B}R or sigma nonspecific receptor are to be avoided with the exception of drugs that are considered absolutely essential for the care of the subject. Treatment with concomitant drugs that are strong inhibitors of CYP3A should be avoided with the exception of antibiotics, antifungals and antivirals that are used as standard of care to prevent or treat infections. If CYP3A inhibitors are used concomitantly, subjects should be closely monitored for AEs.

Precaution should be used in use of gilteritinib with concomitant drugs that are known to prolong QT or QTc intervals.

Precaution should be used in use of gilteritinib with concomitant drugs that are substrates of BCRP, since the transporter has been shown to be inhibited by gilteritinib in in vitro studies.

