7.6 Analysis of Pharmacokinetics

Descriptive statistics (e.g., N, mean, standard deviation, minimum, median, maximum, coefficient of variation [CV], geometric mean, and geometric CV) will be provided for trough plasma concentrations (C_{trough}) of gilteritinib and possible metabolite(s), if appropriate, by treatment, visit and time point.

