7.6 Analysis of PK

PK analysis will be conducted on the PKAS.

Descriptive statistics (e.g., N, mean, standard deviation, minimum, median, maximum, coefficient of variation [CV], geometric mean, and geometric CV) will be provided for trough plasma concentrations (C_{trough}) of gilteritinib, if appropriate, by visit and time point.

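### Later-visit gilteritinib Ctrough summaries mix current doses and strong CYP3A inhibitor use under a first-dose label, so they cannot be read as exposure at the labelled combination dose

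*SAP*

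**What the plan says.** The secondary objective (Protocol 2.1.2) is: "Characterize the pharmacokinetics of gilteritinib and its active metabolites (if appropriate) when given in combination with atezolizumab". Ctrough is a secondary endpoint. Samples are taken before dosing on days 1, 8 and 15 of cycle 1, then on days 1 and 15 of each later cycle up to 6 months (SAP 6.3).

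The grouping rules are these:

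- SAP 7.1: "Pharmacokinetic summaries based on will be presented by actual treatment received". The next sentence reads: "For subjects with dose change, actual treatment refers to the first dose received before dose change". It makes no exception for pharmacokinetics.
- SAP 7.6: descriptive statistics for Ctrough "of gilteritinib, if appropriate, by visit and time point".
- Protocol 7.6: the same statistics "by treatment, visit and time point", for gilteritinib and possible metabolites.
- SAP 7.8: no subgroups.

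Three features of the protocol let conditions change while sampling continues:

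- **Dose.** Gilteritinib may be stepped from 120 to 80 to 40 mg (Protocol 5.1.2.1).
- **Partner drug.** "If 1 treatment is discontinued due to toxicity, the subject may continue on the other as monotherapy until discontinuation criteria is met" (Protocol 2.2.1).
- **Co-medication.** Strong CYP3A inhibitors "should be avoided with the exception of antibiotics, antifungals and antivirals that are used as standard of care to prevent or treat infections" (Protocol 5.1.4).

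The PKAS definition (SAP 5.3) leaves exclusion of subjects or time points to the Classification Specifications and to the pharmacokineticist's discretion. It states no criterion.

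**The concern.** A summary labelled with a dose should describe samples taken on that dose. Here the label is fixed at the first dose, while the dose behind the sample may have fallen by one third or two thirds. The protocol reports approximately dose-proportional pharmacokinetics over 20 to 450 mg, so such a trough is expected to be lower in about the same proportion.

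Inhibitor use pulls the other way. Protocol 1.2.3.2 reports: "Coadministration of gilteritinib with ITZ significantly increased gilteritinib exposure (approximately 2.21-fold) via a reduction in CL/F". Nothing in SAP 7.6 separates those troughs.

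A fall in the tabulated mean over cycles may then reflect only dose reductions, and a rise only anti-infective use. The two can also offset each other, leaving a plausible mean with inflated spread. Anyone quoting the later-visit rows as gilteritinib exposure at the combination dose would be quoting a mixture.

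**Working it through.** The documents give no precision target or sample-size figure for Ctrough, so there is no planned figure to reproduce. The check sizes the mixing from the protocol's own pharmacokinetic figures.

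**Inputs**

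- Dose ratios: 80/120 = 0.667 and 40/120 = 0.333 (Protocol 5.1.2.1), with approximate dose proportionality (Protocol 1.2.3.2).
- Strong CYP3A4 inhibitor: 2.21-fold exposure in healthy adults (Protocol 1.2.3.2). Applying it to troughs in patients is an assumption.
- Half-life: 45 to 159 h (Protocol 1.2.3.2).
- Share of troughs affected: not given in the documents. Assumed range 10% to 50%.

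**How much sampling is exposed.** Reading 6 months as six 28-day cycles gives 3 + 2 × 5 = 13 scheduled troughs, of which 10 fall after cycle 1.

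**Shift in the geometric mean.** With a share f affected, the ratio to the true 120 mg value is 0.667^f, 0.333^f or 2.21^f.

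| Share f | At 80 mg | At 40 mg | On strong inhibitor |
|---|---|---|---|
| 10% | 0.96 | 0.90 | 1.08 |
| 20% | 0.92 | 0.80 | 1.17 |
| 30% | 0.885 | 0.72 | 1.27 |
| 50% | 0.82 | 0.58 | 1.49 |

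SAP 7.6 also reports the arithmetic mean. At f = 20% the dose ratios are 1 − 0.2 × 1/3 = 0.93 and 1 − 0.2 × 2/3 = 0.87. At f = 30% on an inhibitor the ratio is 1 + 0.3 × 1.21 = 1.36.

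**Offsetting.** With 30% at 80 mg and, independently, 30% on an inhibitor, the geometric mean ratio is 0.885 × 1.269 = 1.12. The added log-variance is 0.3 × 0.7 × [ln(2/3)]² + 0.3 × 0.7 × [ln 2.21]² = 0.035 + 0.132 = 0.167. An assumed base geometric CV of 30% then rises to about 54%, and one of 50% to about 69%.

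**Range under one label.** From 0.33 (40 mg, no inhibitor) to 2.21 (120 mg with inhibitor), about 6.6-fold.

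**Small cohorts.** Phase 1 cycle 1 is free of dose reductions but not of inhibitors. One user among 3 subjects moves the arithmetic mean by 1 + 1.21/3 = 1.40; one among 6 by 1 + 1.21/6 = 1.20.

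**Is the dose on the sampling day enough?** The time to 90% of a new steady state is t½ × ln 10 / ln 2. That is 45 × 3.32 / 24 = 6.2 days to 159 × 3.32 / 24 = 22.0 days. Fourteen days after a change, 1 − 2^(−336/45) = 99% to 1 − 2^(−336/159) = 77% of the shift is complete. A trough soon after a step-down therefore belongs fully to neither dose.

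**The case against.** **The objective is descriptive and the tables are by visit.** This stands. In phase 1, Protocol 5.1.2.1 bars gilteritinib reduction in cycle 1, so the day 8 and day 15 troughs are at the assigned dose and follow the day 1 atezolizumab infusion. A reader might infer that the Ctrough tables cannot serve the objective at all; these rows show otherwise. They remain open to inhibitor use, and at a 159 h half-life they are only about 52% (day 8) and 77% (day 15) of steady state. Phase 2 has no such bar in cycle 1, although reduction for myelosuppression requires at least two cycles first.

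**Dose selection is not touched by the first-dose rule.** A reader might infer harm to the RP2D decision, because the DEC reviews pharmacokinetic data. The documents do not support that. Escalation rests on cycle 1 DLTs, the DEC meets after the DLT period, and no reduction can have occurred in a phase 1 subject during it.

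**No atezolizumab effect is being tested.** The study is single arm with no gilteritinib-alone group. Protocol 1.4 calls atezolizumab's interaction potential unknown but expects no meaningful interaction with gilteritinib, and the documents give no effect size for an atezolizumab stop. Troughs after a stop therefore justify a flag, because the objective concerns the combination, but no claim of bias.

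**PKAS exclusions could deal with it.** Partly. The text is wide enough to remove time points, but no criterion is written and the Classification Specifications are not available to check. Exclusion also does not give a valid 80 mg trough its correct label. The listing of dose reductions and interruptions (SAP 7.3.1) permits checking by hand but does not change the summaries.

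**The shares are assumed.** They are. A second step-down requires prior clinical benefit, and strong inhibitors are to be avoided outside anti-infective use, so high shares may not occur. The mislabelling itself does not depend on them.

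**Conclusion.** The point holds for visits after dose reductions become possible. SAP 7.1 attaches the first dose to every later trough, and SAP 7.6 contains nothing that corrects this or separates inhibitor use. At modest assumed shares the geometric mean is off by about 8% (20% at 80 mg), 20% (20% at 40 mg) or 27% in the other direction (30% on a strong inhibitor). These sizes rest on dose proportionality, on carrying an exposure ratio from healthy adults over to patient troughs, and on shares that the documents do not give.

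The consequence is limited to the interpretation of a descriptive secondary endpoint. No test, decision threshold or primary result depends on it. It should be corrected in the SAP before database lock.

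**What to change.** In SAP 7.1 and 7.6:

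1. Except pharmacokinetic summaries from the first-dose rule. Classify each Ctrough by the gilteritinib dose in use throughout a pre-specified run-in before sampling. Justify the run-in against the 45 to 159 h half-life (about 6 to 22 days for 90% of a new steady state).
2. Flag, or tabulate separately, troughs falling within the run-in after a dose change or interruption.
3. Present Ctrough with and without concurrent strong CYP3A inhibitors. Flag moderate inhibitors too, since the protocol reports a 1.43-fold exposure effect for one of them.
4. Flag troughs taken after atezolizumab has stopped.
5. Write these time-point rules into the SAP rather than leaving them to the Classification Specifications.
6. Reconcile SAP 7.6 with Protocol 7.6, which also groups by treatment and allows for metabolites.

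The cost is SAP wording and programming. Dosing records, dosing and sampling times, and concomitant medications with start and stop dates are already collected, and no clinical procedure changes. The downside is smaller numbers per cell at late visits. With sampling every 14 days, a run-in near 22 days sets aside one or two scheduled troughs after each change.

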7.2 Study Population

7.2.1 Disposition of Subjects

The following subject data will be presented:

- Number and percentage of subjects with informed consent, discontinued before allocation to treatment, allocated to treatment (overall only);
- Number and percentage of subjects allocated to treatment in each analysis set;
- Number and percentage of subjects completed and discontinued treatment, by primary reason for treatment discontinuation;
- Number and percentage of subjects completed and discontinued the study, by primary reason for study discontinuation;
- Number and percentage of subjects completed and discontinued the post-study period, by primary reason for post-study period discontinuation;

7.2.2 Protocol Deviations

Protocol deviations as defined in the study protocol (Section 8.3 Major Protocol Deviations) will be assessed for all subjects allocated to treatment. The number and percentage of

subjects meeting any criteria will be summarized for each criterion and overall as well as by study site. Subjects deviating from a criterion more than once will be counted once for the corresponding criterion. Any subjects who have more than one protocol deviation will be counted once in the overall summary. A data listing will be provided by site and subject.

The protocol deviation criteria will be uniquely identified in the summary table and listing. The unique identifiers will be as follows:

- PD1 - Entered into the study even though they did not satisfy entry criteria,
- PD2 - Developed withdrawal criteria during the study and was not withdrawn,
- PD3 - Received wrong treatment or incorrect dose,
- PD4 - Received excluded concomitant treatment.

7.2.3 Demographic and Other Baseline Characteristics

Demographic and other baseline characteristics will be summarized for the SAF. Descriptive statistics will include number of subjects, mean, standard deviation, minimum, median and maximum for continuous endpoints and frequency and percentage for categorical endpoints.

Number and percentage of subjects allocated to treatment in each country and site will be presented for the SAF.

Descriptive statistics for age, weight, body mass index (BMI), height, and prior FLT3 inhibitor (gilteritinib, quizartinib, crenolanib) at study entry will be presented. Frequency tabulations for sex, ethnicity, region, age group (< 65 years vs. ≥65 years) and race will be presented. Demographics and baseline characteristics will be summarized for the SAF.

Frequency tabulations for AML disease history including AML subtype as classified by World Health Organization (WHO) classification and French-American-British (FAB) classification, risk status, antecedent hematological disorder, central nervous system leukemia, FLT3 mutation status will be presented for the SAF.

Medical history other than AML and conditions existing at baseline will be coded in MedDRA and summarized by System Organ Class (SOC) and Preferred Term (PT) as well as by PT alone for the SAF. Baseline conditions are defined as those ongoing at the time of informed consent or arise following the time of informed consent and before the first dose of study drug. For ongoing medical conditions, Common Terminology Criteria for Adverse Events (CTCAE) grade will be provided in listing.

Results from lumbar puncture and MUGA scan, if performed, will be provided in listing.

7.2.4 Previous and Concomitant Medications

Previous medications are coded with World Health Organization – Drug Dictionary (WHO-DD), and will be summarized by therapeutic subgroup (Anatomical Therapeutic Chemical [ATC] 2nd level) and chemical subgroup (ATC 4th level) and preferred WHO name for the SAF.

As with previous medication, concomitant medication will be summarized by therapeutic subgroup (ATC 2nd level), chemical subgroup (ATC 4th level) and preferred WHO name for the SAF. Subjects taking the same medication multiple times will be counted once per medication. A medication which can be classified into several chemical and/or therapeutic subgroups is presented in all chemical and therapeutic subgroups.

Concomitant medication will also be summarized for SAF and presented in decreasing order of frequency based on the total number of subjects who took each medication.

7.2.5 Previous and Concomitant Non-Medication Therapy

Frequency tabulations of subjects with previous non-medication therapy and reason for use will be presented for SAF. Number of previous non-medication therapy received per subject will be summarized using descriptive statistics.

Concomitant non-medication therapy will also be summarized as previous non-medication therapy.

7.3 Study Drugs

7.3.1 Exposure

The following information on drug exposure will be presented for the SAF:

- Descriptive statistics for cumulative amount of the drug subject was exposed to and average daily dose; and
- Number and percent of subject with dose increase, decrease or interruptions.

Duration of exposure will be summarized in two ways.

- Descriptive statistics will be presented.
- Exposure time will be categorized according to the following categories:
 - less than 3 months
 - at least 3 months, less than 6 months
 - at least 6 months, less than 12 months
 - at least 12 months, less than 24 months
 - 24 months or more
 - Unknown.

Counts and percentages of subjects in each of these categories will be summarized for the SAF.

Listing of subjects with dose reduction and interruption will also be provided for SAF.

Descriptive statistics for duration of exposure, cumulative amount of the drug subject was exposed to average daily dose, dose intensity and relative dose intensity will be presented for study drug.

7.3.2 Treatment Compliance

Treatment compliance of gilteritinub is defined as the total number of doses of gilteritinub actually taken by the subject divided by the number of doses of study drug

expected to be taken during the study multiplied by 100. Treatment compliance of Atezolizumab is defined as total amount of Atezolizumab actually consumed by amount of study drug should been taken multiplied by 100. Descriptive statistics for study drug compliance will be presented by dose for the entire study period for the SAF. Overall compliance will be examined for subjects in the SAF whose total study drug count and first and last days of treatment are known.

Percent overall compliance will be summarized in two ways for the SAF:

- Descriptive statistics will be presented by cohort and dose level.
- Percent compliance will be categorized according to the following categories:
 - less than 50%
 - at least 50%, less or equal to 80%
 - greater than 80%
 - Unknown.

Overall compliance will be provided in listing.

7.4 Analysis of Efficacy

Efficacy analysis will be conducted on the FAS.

7.4.1 Analysis of Primary Efficacy Endpoint

The CRc rate will be evaluated according to Simon's minimax two-stage design (Simon, 1989). The null hypothesis that the true CRc rate is 50% will be tested against a one-sided alternative.

In stage I, a total of 22 subjects will be evaluated. If there are 11 or fewer subjects with CRc from these 22 subjects by the end of cycle 2, the study will be stopped. Otherwise, 27 additional subjects will be accrued for a total of 49 subjects evaluable for calculation of CRc rate. The null hypothesis will be rejected if 32 or more subjects with CRc are observed in the 49 subjects by the end of cycle 2. This design yields a one-sided type I error rate of 0.025 and power of 80% when the true CRc rate is 70%.

The CRc (CR + CRp + CRi) rate will be summarized and its 95% confidence interval will be constructed by Clopper-Pearson method.

